8.6 Human Biological Sample for Biomarkers

8.6.1 Collection of Mandatory Samples for Biomarker Analysis

By consenting to participate in the sub-study, the participant consents to the mandatory research components of the study.

Samples for biomarker research are required and will be collected from participants, as specified in the SoAs (see Section 1.3). Nasopharyngeal swabs will be collected for virologic assessments. Saliva samples may be collected at site Illness Visits and by the participants during the home collection period. These biomarker measurements will support understanding of potential correlates of protection, duration of immune responses, and correlations between pharmacodynamics and ADA immunogenicity. Details for sample collection, processing, and testing will be provided in the Laboratory Manual.

Any results from such analyses may be reported separately from the sub-study CSR.

8.6.1.1 Virologic Assessments

Participants who have not received a negative SARS-CoV-2 RT-PCR test result \leq 3 days before study entry will require a negative result from a SARS-CoV-2 rapid antigen test on SS-D1 to be included into the sub-study.

Nasopharyngeal swabs will also be assessed by authorized RT-PCR assays for the detection of SARS-CoV-2 by the central laboratories according to the time points specified in the SoA (Section 1.3). Instructions for obtaining and processing NP swab samples are provided in the Laboratory Manual. The full-length S gene (AA 1-1274) from SARS-CoV-2-positive nasal samples may be amplified using a standard, single tube population-based RT-PCR method and sequenced by next-generation sequencing (NGS) at IL-D1, IL-D14, IL-D21, and IL-D28. Amino acid variation across the full-length S protein sequence may be determined and reported separately from the CSR. Amino acid changes identified by genotypic analyses of the

S trimer protein ectodomain (AA 20-1213) can be evaluated by either a spike trimer binding affinity assay and/or a recombinant SARS-CoV-2 Spike-pseudovirus neutralization assay. Additional details on clinical virology analyses, including molecular surveillance of the S protein in global circulation will be provided in the Virology Analysis Plan.

Local and central assessments should be collected per the schedule of activities; where both local and central assessments are listed both are required and should be collected. Additionally, a validated multiplexed respiratory panel may be utilized to assess for the presence of other respiratory pathogens in NP swabs in a central laboratory operated on behalf of the Sponsor at IL-D1.

8.7 Optional Genomics Initiative Sample

Genomics sampling is not applicable in this sub-study.

8.8 Medical Resource Utilization and Health Economics

Medical resource utilization and health economics are not applicable in this sub-study.

9 STATISTICAL CONSIDERATIONS

9.1 Statistical Hypotheses

The primary objective of this sub-study is to assess the safety and tolerability of repeat doses of AZD7442 300 mg and 600 mg IM. No hypotheses will be tested.

9.2 Sample Size Determination

Approximately 500 participants will be enrolled in the sub-study to receive repeat doses of AZD7442. If the true adverse event rate is 1%, the probability of observing at least one AE in

500 participants is > 99%. The incidence of 1% is the lower limit of the category of common AEs (between infrequent and frequent AEs) by the Council for International Organizations of Medical Sciences (CIOMS) Working Group (CIOMS 1999).

Participants in the sub-study will received repeat dosing of AZD7442 as outlined in Figure 1. Group level recruitment caps may be placed to ensure at least 50 subjects complete the study with their assigned dose and valid samples for analysis. A study sample of 50 or more participants will have greater than a 90% probability to estimate a 95% confidence interval within 60% to 140% of the assumed true geometric mean for pharmacokinetic parameters. This calculation assumes a conservative estimated standard deviation of 25, true geometric mean of 20 and a half width confidence interval of 8. The current number of participants in the sub-study (503) will provide a sufficient sample assuming participants are evenly distributed across the 3 groups. The addition of Group 3 will create 4 possible dosing cohorts, based on the how many doses of 300mg AZD7442 received prior to entering Group 3 and whether or not this was followed by a further two doses of 600mg AZD7442:

Group 1

Cohort 1: AZD7442 300 mg, 300 mg

Group 2

Cohort 2: Placebo, AZD7442 300 mg, 300 mg

Group 3

- Cohort 3 (from Group 1): AZD7442 300 mg, 300 mg, 600 mg, 600 mg
- Cohort 4 (From Group 2): Placebo, AZD7442 300 mg, 600 mg, 600 mg

9.3 Populations for Analyses

The following populations are defined in Table 14.

Table 14 Populations for Analysis

Population/Analysis set	Description
Safety analysis set	The safety analysis set consists of all participants who have received at least one dose of IMP in the sub-study.
Safety pre-exposure analysis set	The safety pre-exposure analysis set will include all participants in the safety analysis set who were not SARS-CoV-2 RT-PCR-positive at baseline in the parent study.
Pharmacokinetic analysis set	All participants in the safety analysis set who received AZD7442 and from whom PK blood samples are assumed not to be affected by factors such as protocol violations and who had at least one quantifiable serum PK observation post dose will be included in the PK analysis dataset.

IMP, investigational medicinal product; PK, pharmacokinetic; RT-PCR, reverse transcriptase polymerase chain reaction; SARS-CoV-2; severe acute respiratory syndrome-coronavirus 2.

9.4 Statistical Analyses

All results will be summarized with descriptive statistics by cohort. Categorical variables will be summarized using frequency and percentages, where the denominator for calculation is the underlying analysis set population, unless otherwise stated. Continuous variables will be summarized with descriptive statistics of number of available observations, mean, standard deviation, median, minimum and maximum, and quartiles where more appropriate.

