3 OBJECTIVES AND ENDPOINTS

Table 7 lists the objectives and endpoints for the PROVENT repeat dose sub-study.

Table 7 Objectives and Endpoints for Repeat Dose Sub-Study

Objective	Endpoint
Primary	
To evaluate the safety and tolerability of repeat doses of AZD7442 300 mg and 600 mg IM	AEs, SAEs, MAAEs, and AESIs post repeat dose of IMP
Secondary	
To evaluate the pharmacokinetics of repeat doses of AZD7442 300 mg and 600 mg IM	Serum AZD7442 concentrations following repeat dosing. PK parameters if data permit following repeat dosing
To evaluate ADA responses to repeat doses of AZD7442 300 mg and 600 mg IM in serum	Incidence of ADA to repeat doses of AZD7442 in serum
To determine anti-SARS-CoV-2 nAb levels in serum following repeat doses of AZD7442 300 mg and 600 mg IM	Post-treatment GMTs and GMFRs from baseline values after a repeat IM dose in SARS-CoV-2 nAbs (wild-type assay or pseudo-neutralization assay)
Exploratory	
PPD	PPD

ADA, antidrug antibody; AE, adverse event; AESI, adverse event of special interest; COVID-19, coronavirus disease 2019; GMT, geometric mean titers; GMFR, geometric mean fold rise; IM, intramuscular; IMP, investigational medicinal product; MAAE, medically attended adverse event; nAb, neutralizing antibody; PK, pharmacokinetic; RT-PCR, reverse transcriptase polymerase chain reaction; SAE, serious adverse event; SARS-CoV-2, severe acute respiratory syndrome-coronavirus 2.

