4.2 Scientific Rationale for Study Design

This sub-study of the ongoing PROVENT parent study was designed to rapidly obtain clinical safety, PK, and immunogenicity data after repeat AZD7442 dosing in individuals who cannot receive a COVID-19 vaccine or are not expected to be adequately protected by a vaccine (ie, the target population for repeat dosing). This sub-study will aim to enrich the PROVENT study population with individuals who may benefit from a repeat dose of AZD7442 by targeting appropriate participant groups enrolled in the parent study (see Section 5.1).

The dosing intervals of approximately 6 months and 12 months to be evaluated in this study are based upon the extended half-life of AZD7442 and expected need for repeat dosing in clinical practice.

To generate repeat dose data as rapidly as possible, participants randomized to the PROVENT parent study who meet the sub-study inclusion criteria will be offered participation in the sub-study when it is initiated. This will result in some participants receiving a repeat dose as early as 10 months after the first dose in the parent study.

- Participants assigned to the 12-month dosing interval (Group 1) will be derived from the AZD7442 arm in the parent study. These participants will enter the sub-study and receive their second dose 12 ± 2 months after receiving their first dose in the parent study, (see Figure 1). An interim analysis will take place when a minimum of 50 participants have been followed until Day 29.
- Participants assigned to the 6-month dosing interval (Group 2) will be derived from the
 placebo arm in the parent study. This group will receive their first dose of AZD7442 upon
 entering the sub-study followed by a repeat dose at approximately 6 months (see

Figure 1). This group will generate data supporting assessment of a shorter repeat dosing time interval of the long-acting AZD7442 formulation.

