9.4.1 Safety: Primary Endpoint

9.4.1.1 Primary Endpoint(s)

The safety of AZD7442 will primarily be assessed by:

- Incidence of AEs
- Incidence of SAEs
- Incidence of MAAEs
- Incidence of AESIs

The AE severity will be graded according to Appendix B and coded using the most recent version of the Medical Dictionary for Regulatory Activities. Adverse events will be presented for each dosing interval group by system organ class and preferred term. Summaries will include the number and percentage of participants reporting at least one event, number of events, and exposure adjusted rates, where appropriate.

An overview of AEs will be presented for each group, including the number and percentage of participants with any AE and SAEs. Summaries will present the relationship to IMP as assessed by the Investigator, maximum intensity, seriousness, and death.

A listing will cover details for each individual AE.

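### The primary endpoint is AEs after a repeat dose, but the safety set and AE summaries do not isolate that time in parent-placebo participants, nor 600 mg time in Cohort 3

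*Protocol*

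**What the plan says.** - **Objective and endpoint (Protocol Section 3, Table 7).** The primary objective is "To evaluate the safety and tolerability of repeat doses of AZD7442 300 mg and 600 mg IM". Its endpoint is "AEs, SAEs, MAAEs, and AESIs post repeat dose of IMP".
- **Analysis set (Section 9.3, Table 14).** "The safety analysis set consists of all participants who have received at least one dose of IMP in the sub-study". No repeat-dose set is defined.
- **Denominator (Section 9.4).** For categorical variables, "the denominator for calculation is the underlying analysis set population, unless otherwise stated".
- **Reporting unit.** Section 9.4: "All results will be summarized with descriptive statistics by cohort". Section 9.4.1.1: "Adverse events will be presented for each dosing interval group by system organ class and preferred term", and "An overview of AEs will be presented for each group". Exposure-adjusted rates are promised where appropriate, without a definition of exposure over several doses.
- **Which dose is the repeat dose.** Section 9.5 treats the SS-D1 dose as a repeat dose for participants who had AZD7442 in the parent study. Section 4.2 has the parent-placebo participants take their first AZD7442 dose on "entering the sub-study followed by a repeat dose at approximately 6 months". Section 6.1.1 describes both 600 mg doses as repeat doses.
- **Time windows.** Section 8.3.1 collects AEs from IMP administration to the last visit. Sections 4.1 and 4.2 set the length of safety follow-up from the last dose. None of these says where an AE table starts counting.
- **SAP.** The supplied SAP covers the single-dose parent study.

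**The concern.** The endpoint depends on a particular dose having been given. The analysis set and summaries do not apply that condition, and this matters in two places.

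First, in Cohorts 2 and 4 the period from SS-D1 to SS-D183 is first-dose time. If AEs are tabulated from SS-D1, first-dose events enter a result labelled as post repeat dose. If only later events are counted, participants who never received the SS-D183 dose still sit in the denominator. The protocol gives routes to this: Section 7.1 keeps participants in the study after IMP is discontinued, and Table 10 rules out further AZD7442, but not follow-up, after COVID-19 treatment with another monoclonal antibody.

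Second, Cohort 3 receives a repeat 300 mg dose at SS-D1 and 600 mg from SS-D183. Both count as repeat doses, so no reading of the endpoint separates them. Injection site reactions show the effect: they are an AESI (Section 8.3.4), and the volume per injection is 1.5 mL at 300 mg and 3 mL at 600 mg (Table 9). A participant whose only reaction followed the SS-D1 dose would appear in a column that readers may take as 600 mg experience. Cohort 3's earlier time is also selected, because Group 3 forms only at SS-D183, from those still on study who consent (Section 4.1).

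At stake are the 600 mg part of the primary objective and the Section 4.2 aim of comparing safety after a repeat dose with safety after a single dose.

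**Working it through.** **Plan's own figures.** Section 9.2 states a probability above 99% of seeing at least one AE in 500 participants at a 1% rate: 1 − 0.99^500 = 99.3%, which agrees. Section 4.1 gives durations of 457, 639 and 548 days. Groups 1 and 2 reproduce as 1 + 456 = 457 and 183 + 456 = 639.

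**Inputs.** Dosing days are SS-D1, SS-D183 and SS-D366; the last days are SS-D457, SS-D639 and SS-D548 (Section 1.3, Tables 2 to 4). Full scheduled follow-up is assumed and visit windows are ignored.

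**Days by period**
- SS-D1 to SS-D183: 183 − 1 = 182.
- First 600 mg dose to end: 548 − 183 = 365.
- Total, Cohort 2: 639 − 1 = 638. Total, Cohorts 3 and 4: 548 − 1 = 547.

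| Cohort | First 300 mg | Repeat 300 mg | 600 mg |
|---|---|---|---|
| 1 | 0 | 456 | 0 |
| 2 | 182 | 456 | 0 |
| 3 | 0 | 182 | 365 |
| 4 | 182 | 0 | 365 |

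**Counting from SS-D1.** Time before any repeat dose is 182/638 = 28.5% in Cohort 2, 182/547 = 33.3% in Cohort 4, and zero in Cohorts 1 and 3.

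**Counting strictly after the first repeat dose.** Those shares fall to zero. Cohort 3 still has 182/547 = 33.3% of its time at repeat 300 mg before any 600 mg dose.

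**If Cohorts 3 and 4 are pooled as Group 3, counting strictly.** With share f drawn from Group 1, the 300 mg share is 182f / (547f + 365(1 − f)).
- f = 0.5, the planned even draw: 91/456 = 20.0%.
- f = 0.4 or 0.6 (assumed range): 72.8/437.8 = 16.6% or 109.2/474.2 = 23.0%.

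**Denominator, Cohorts 2 and 4 only.** The documents give no rate of missed SS-D183 doses. If a share d misses it and only post-repeat events are counted, a true incidence p is reported as p(1 − d). For p = 10% and d = 5%, 10% or 20% (all assumed), the result is 9.5%, 9.0% or 8.0%.

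**Carry-over.** Five half-lives are 456 days in Section 4.2 and one year in Table 10. Under simple first-order decay, the share of the SS-D1 dose left at SS-D183 is 0.5^(182/91.2) = 25.1% or 0.5^(182/73) = 17.8%. Dose periods are therefore not pharmacologically clean.

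**Size of the 600 mg base.** The protocol's amendment rationale mentions about 150 participants for Group 3. At a 1% rate, 1 − 0.99^150 = 77.9%, against 99.3% for all 500.

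**The case against.** The strongest reply has five parts.

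1. *Summaries by cohort already separate the regimens.* They separate participants with different sequences, but not periods within a participant. Cohorts 2, 3 and 4 each contain two dose periods. It does stand that, under the by-cohort wording, Cohorts 3 and 4 are not pooled, so the 20.0% figure arises only if the group wording of Section 9.4.1.1 is followed.
2. *Follow-up is anchored to the last dose, which in Groups 1 and 2 is the repeat dose.* This is correct and shows the design intent. It fixes how long participants are followed, not which events enter a table.
3. *Time origins and person-time belong in the SAP.* The parent SAP does define exposure (Section 18.1), as running from the dose to the end of study, which suits a single dose only. A sub-study SAP may settle the matter. A reader might infer that no planned table will separate the periods; the documents do not support that, because the protocol contains no table shells and that SAP is not available. What can be shown is that the protocol's own set and denominator do not match its endpoint.
4. *Nothing is tested, and the data can be re-cut.* True: Section 9.1 has no hypotheses, Section 8.3.2 collects AE dates and times, and Section 9.4.1.1 lists every AE. This limits the harm, although the descriptive tables are the whole primary analysis.
5. *Attribution by period is imperfect.* Also true, given the carry-over. Restricting parent-placebo participants to those who received the SS-D183 dose also conditions on reaching that day.

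Contact after SS-D183 is not simply sparser, either. It moves from weekly to monthly (Section 8.1.1), but Group 3 adds a safety call one week after each 600 mg dose (Table 4).

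**Conclusion.** The mismatch is real and should be fixed, within limits. For Cohorts 2 and 4 the stated set and denominator do not give incidence after a repeat dose, and 28.5% and 33.3% of scheduled days precede one. For Cohort 3 the denominator is right, because the SS-D1 dose is already a repeat dose, but 33.3% of scheduled days are repeat 300 mg time that the protocol does not separate from 600 mg time. Cohort 1 is unaffected.

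A reader might infer that every primary safety percentage is wrong. The documents do not support this: parent-AZD7442 participants all have a repeat dose by definition of the safety set. Nor are the day shares a measure of bias in any reported incidence; they are shares of scheduled follow-up, assuming no dropout. The denominator effect cannot be sized from the documents, and Section 7.2 expects withdrawal to be uncommon.

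The undefined exposure for adjusted rates and the three names for the reporting unit are wording gaps of lesser weight.

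**What to change.** In Sections 9.3 and 9.4, or in the sub-study SAP if that is where these rules sit:

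1. Keep the full safety set for overall tables. Add a repeat-dose table counting AEs from each participant's first repeat dose (SS-D1 for parent-AZD7442, SS-D183 for parent-placebo), with those who received that dose as the denominator. Note that for parent-placebo participants this conditions on reaching SS-D183.
2. Tabulate AEs and person-time by period: first 300 mg, repeat 300 mg, and from the first 600 mg dose. Use these periods for the exposure-adjusted rates. Footnote the carry-over (about 18% to 25% of the SS-D1 dose at SS-D183 under simple decay) and the contact schedule, including the Group 3 one-week calls.
3. Start the 600 mg tables at the first 600 mg dose. Show time before SS-D183 by original group (Cohorts 1 and 3 together, 2 and 4 together), so that it is not selected on later entry to Group 3.
4. As a minor point, use one name for the reporting unit and say whether Cohorts 3 and 4 are pooled.

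The cost is some wording and a few more tables, with no new data. The price is a smaller and shorter base for the 600 mg figures: Group 3 only, about 365 days each.

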By preparing for new and future SARS-CoV-2 variants of concern (i.e., BA.4 and BA.5 currently increasing in prevalence) this protocol is being updated to include a 600 mg dose with an administered frequency of 6 months over 12 months to maintain the efficacy. The 600 mg IM dose selected for this sub-study extension is based on the 600 mg dose administered in the TACKLE study, and 600 mg AZD7442 is authorized for emergency use in the USA since 24 February 2022; both of which demonstrated a generally safe and well-tolerated safety profile.

Group level recruitment caps may be placed to ensure 50 or more participants complete the study with their assigned dose and valid samples. Approximately 150 participants from the USA may be selected from the existing participants enrolled on the sub-study with an approximately even distribution coming from the 2 existing groups to receive repeat doses

of 600 mg IM. This approach will maintain a balanced sample across the 3 groups to support descriptive analysis for PK and safety at each dose schedule. Immunosuppressed participants will be prioritized to be enrolled into the new 600 mg IM dosing study group. This is in line with the indication for which the product is currently authorized for emergency use in the USA.

Specific changes of the sub-study CSP addendum are as follows:

Section 1.1 (Synopsis)

The sub-sections were updated to include the new 600 mg repeat dose participant study arm, extended study duration, and interim analyses. In addition the Cardiovascular Event Adjudication Committee was added to align with other AZD7442 studies.

Section 1.2 (Schematic)

The schematic has been updated to include the additional repeat dose participant arm and extended study duration.

Section 1.3 (Schedule of Activities)

A new Schedule of Activity table has been included for extended sub-study treatment and follow-up periods of the additional repeat dose participant groups. In addition the COVID-19 monitoring schedule for all groups were aligned.

Section 2.3.1 (Risk Assessment)

The table was updated to align with the current Investigator Brochure and SAE occurrence updated

Section 3 (Objectives and Endpoints)

The section has been updated to include the additional repeat dose participant arm.

Section 4.1 (Overall Study Design)

The section has been updated to include the additional repeat dose participant arm and extended study duration.

Section 4.2 (Scientific Rational for the Study Design)

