At 6 months (SS-D183), a subset of participants from USA sites in Group 1 and Group 2 who consent to receive additional AZD7442 600 mg doses (approximately evenly distributed between groups) approximately every 6 months and will be assigned to a new arm - Group 3. All other participants will continue in the sub-study according to their originally assigned dosing interval group schedule. The addition of Group 3 will create 4 possible dosing cohorts, based on the how many doses of 300mg AZD7442 received prior to entering Group 3 and whether or not this was followed by a further two doses of 600mg AZD7442:

Group 1

Cohort 1: AZD7442 300 mg, 300 mg

Group 2

Cohort 2: Placebo, AZD7442 300mg, 300 mg

Group 3

- Cohort 3 (from Group 1): AZD7442 300 mg, 300 mg, 600 mg, 600 mg
- Cohort 4 (From Group 2): Placebo, AZD7442 300 mg, 600 mg, 600 mg

Group level recruitment caps may be placed to ensure 50 or more participants complete the study with their assigned dose and valid samples.

Group 1 and Group 2 will undergo safety follow-up for 456 days after the last dose of AZD7442, and Group 3 will undergo safety follow-up for 183 days after the last dose of AZD7442. The total duration of the sub-study will be 457 days for Group 1, 639 days for Group 2, and 548 days for Group 3.

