• Participants assigned to the 18-month dosing schedule (Group 3) will be derived from a subset of participants at the USA sites in Group 1 and Group 2 in the sub-study (approximately evenly distributed between groups). This group will receive 2 doses of 600 mg IM AZD7442 at approximately 6 month intervals starting at SS-D183, following consent to the amended sub-study (see Figure 1), to align the dosing schedule per the FDA Fact sheet. This group will generate additional safety, PK, and immunogenicity data for longer-term repeat dosing time intervals of the long-acting AZD7442 formulation.

Evaluation of the safety, PK, and ADA immunogenicity of repeat dosing with AZD7442 will inform the following:

- Whether repeat dosing at different dosing intervals will maintain the serum concentrations of AZD7442 associated with protection against symptomatic disease in the parent study.
- Whether the safety profile and immunogenicity (ADA) profile after a repeat AZD7442 dose are comparable to the safety profile and immunogenicity profile observed after a single AZD7442 dose.

To provide safety data on AZD7442 for 5 half-lives, safety endpoints will be collected for 456 days after the last dose of IMP in Group 1 and Group 2.

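### Cohorts 3 and 4 are defined at SS-D183 but summarised without an SS-D183 time origin, so deaths, withdrawals and dose-ending reactions before that visit can count only in Cohorts 1 and 2

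*Protocol*

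**What the plan says.** Protocol Section 4.1 forms Group 3 part-way through the sub-study: "At 6 months (SS-D183), a subset of participants from USA sites in Group 1 and Group 2 who consent to receive" the 600 mg doses are moved to a new arm. For the rest, "All other participants will continue in the sub-study according to their originally assigned dosing interval group schedule". Cohort 3 comes from Group 1, Cohort 4 from Group 2, and those who do not move form Cohorts 1 and 2. The amendment rationale at the front of the protocol adds: "Immunosuppressed participants will be prioritized to be enrolled into the new 600 mg IM dosing study group".

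On analysis, Section 9.4 says "All results will be summarized with descriptive statistics by cohort", with percentages "where the denominator for calculation is the underlying analysis set population, unless otherwise stated". Table 14 in Section 9.3 defines the set: "The safety analysis set consists of all participants who have received at least one dose of IMP in the sub-study". That set includes people lost before SS-D183.

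Three other places bear on this.
- Sections 9.4.1.1 and 9.4.2.2 present AEs and ADA by dosing interval group rather than by cohort. Section 9.4.1.1 adds exposure-adjusted rates where appropriate and lists death in the AE overview.
- Table 7 in Section 3 defines the primary endpoint as events after a repeat dose.
- The SAP supplied is for the parent single-dose study (SAP Section 1) and has no rule for the sub-study cohorts.

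**The concern.** Cohort membership is settled 182 days after SS-D1 by a condition that only people still in the sub-study can meet. If results are then summarised from SS-D1 under that later label, Cohorts 3 and 4 carry six months in which death or withdrawal could not have occurred. The same holds for reactions that end dosing. Appendix E (Table 15) has severe reactions end IMP permanently, and Table 10 ends further AZD7442 after treatment of COVID-19 with another monoclonal antibody. Such participants cannot go on to the 600 mg doses.

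The primary objective covers both 300 mg and 600 mg, and with no hypothesis tests planned these descriptive tables are the safety result. An artefact of classification would go straight into them.

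**Working it through.** **The plan's own figure.** Section 9.2 gives a probability above 99% of seeing at least one AE in 500 participants at a true rate of 1%: 1 − 0.99^500 = 0.9934. This reproduces. It concerns the whole sample and says nothing about how events are divided among cohorts.

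**Inputs from the documents.**
- 503 participants (Section 9.2). An even split is assumed: 251.5 per entry group.
- About 150 move to Group 3 (amendment rationale), so 75 per entry group. Range tried: 25 (from 50 in Group 3) to 84 (from 503/3, about 168).
- Durations of 457, 639 and 548 days for Groups 1, 2 and 3 (Section 4.1). After SS-D183 this leaves 274, 456 and 365 days.

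**Assumptions.** The documents give no death or dropout rate. I take a risk r over the first 182 days of 2% (range 0.5% to 10%) and one constant hazard for everyone, so 600 mg has no true effect.

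**Cohort 1 against Cohort 3 at r = 2%.**
1. h = −ln(0.98)/182 = 0.000111 per day.
2. Early losses in Group 1: 251.5 × 0.02 = 5.03, all left in Cohort 1.
3. Still in follow-up at SS-D183: 246.47. Of these 75 move and 171.47 stay.
4. Later losses in Cohort 1: 171.47 × (1 − e^(−274h)) = 171.47 × 0.02996 = 5.14.
5. Cohort 1: (5.03 + 5.14)/(251.5 − 75) = 10.17/176.5 = 5.76%.
6. Cohort 3: 1 − e^(−365h) = 3.97%, although its total follow-up is longer than Cohort 1's.

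Cohort 2 against Cohort 4 uses the same steps with 456 days for Cohort 2. Part of that gap is Cohort 2's longer follow-up.

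| r = 2%, 75 moving | Percentage | Ratio | Rate from SS-D1 per 100 person-years | Ratio | Rate from SS-D183 | Ratio |
|---|---|---|---|---|---|---|
| Cohort 3 vs 1 | 3.97 vs 5.76 | 0.69 | 2.69 vs 4.76 | 0.56 | 4.05 vs 4.05 | 1.00 |
| Cohort 4 vs 2 | 3.97 vs 7.64 | 0.52 | 2.69 vs 4.57 | 0.59 | 4.05 vs 4.05 | 1.00 |

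Over all risks and Group 3 sizes tried, percentage ratios are 0.67 to 0.79 (Cohort 3/1) and 0.50 to 0.60 (Cohort 4/2). Rate ratios from SS-D1 are 0.52 to 0.65. Counting from SS-D183 gives 1.00 every time. Exposure adjustment from SS-D1 therefore does not remove the artefact; a split at SS-D183 does.

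**Non-fatal AEs.** These do not in general bar entry to Group 3. With equal incidence of 10% to 50% per six months (assumed), the cumulative proportion over d days is 1 − e^(−hd).
- If all sub-study AEs are kept under the final cohort, Cohort 3/1 is 1.06 to 1.17 and Cohort 4/2 is 0.88 to 0.96.
- If Group 3 counts only from SS-D183 while the others count from SS-D1, the ratios are 0.82 to 0.91 and 0.62 to 0.82.

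At 30%, for example, Cohort 1 has 0.591 over 456 days. Cohort 3 has 0.658 over 547 days (ratio 1.11) or 0.511 over 365 days (ratio 0.86). The sign depends on a time origin the plan does not state.

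**The case against.** The strongest reply is that Section 9.4.1.1 already presents AEs by dosing interval group, a term Section 4.1 uses for Groups 1 and 2. If it means entry group, the AE tables are free of this selection. That is a fair reading, but it conflicts with the by-cohort sentence. It would also pool 300 mg and 600 mg time after SS-D183 within each entry group. If the term includes Group 3, which Section 4.2 gives its own dosing schedule, the selection returns. Either way a rule is needed.

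Second, the primary endpoint counts events after a repeat dose. For participants from Group 2 that starts at SS-D183, so read literally Cohort 2 against Cohort 4 escapes the problem. This stands for that pair if the endpoint wording governs over the any-dose safety set; the plan does not say which does. It does not help Cohort 1 against Cohort 3, whose repeat dose is at SS-D1. Nor does the plan say where a Group 2 participant lost before the second dose is counted, since that person does not match Cohort 2's dosing sequence.

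Third, the analysis is descriptive, and a rule may exist in a document not supplied. It is true that no test is distorted and that the fault is an omitted rule, but the protocol sentence as written is the only rule stated.

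A reader might infer that the 600 mg arm will look safer overall. The documents do not support that: the non-fatal AE direction is open, and prioritising immunosuppressed participants may raise Group 3's rates. A reader might also treat Group 1 against Group 2 before SS-D183 as a randomised comparison of second with first dose. It is not. Both groups are volunteers at a subset of sites, still in the parent study 12 ± 2 months after dosing, and those past Day 366 are unblinded before assignment. Finally, the balanced sample mentioned in the amendment rationale is best read as balance in numbers, so it is not a false claim of comparability.

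**Conclusion.** The point holds for deaths, withdrawals and dose-ending reactions. As written, the plan places all of these that occur before SS-D183 outside the 600 mg cohorts. With no true difference, this gives rate ratios of about 0.52 to 0.65 from SS-D1. These sizes rest on assumed six-month risks of 0.5% to 10%, a constant common hazard and an even split by entry group; the mechanism does not depend on them.

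For non-fatal AEs no direction can be claimed. It depends on the unstated time origin, unequal follow-up and the case mix of Group 3. For participants from Group 2, the effect on the primary endpoint depends on whether Table 7 or Table 14 governs. Even with the time origin fixed, post-SS-D183 contrasts remain non-randomised, because Group 3 is USA-only and immunosuppressed participants are prioritised for it.

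**What to change.** In Section 9.4, replace the by-cohort sentence with three rules.
1. SS-D1 to SS-D183: summarise all participants by entry group (Group 1 or Group 2), regardless of later transfer to Group 3.
2. From SS-D183: summarise Cohorts 1 to 4 among participants still in follow-up at that visit, counting events and person-time from it. Show Cohorts 1 and 2 also for USA sites only.
3. Reconcile by cohort (Section 9.4) with dosing interval group (Sections 9.4.1.1 and 9.4.2.2), and the post-repeat-dose endpoint (Table 7) with the any-dose safety set (Table 14). State where a Group 2 participant lost before the second dose is counted.

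Section 4.2 asks whether safety and ADA "after a repeat AZD7442 dose are comparable to the safety profile" and ADA profiles after a single dose. The Group 1 against Group 2 table from rule 1 may be described as the closest internal reference for that question, but not as a randomised comparison. Between-group confidence intervals are optional.

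The cost is a wording change and a few more tables from data already collected, with smaller denominators in the restricted tables.
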